7. STUDY CONSIDERATIONS

Most of the Boostrix exposures during pregnancy will occur at 27 weeks gestation or later. As such, we expect pregnancy outcomes that occur earlier in pregnancy such as spontaneous abortion and therapeutic abortion to be rare in our study. Furthermore, while we will describe the frequency of congenital anomalies among the exposed and unexposed cohorts, we note that the most plausible time period for development of congenital anomalies is during early pregnancy (35). Cautious interpretation of maternal Boostrix immunization and congenital anomalies is warranted.

One potential limitation is that the exposed (Boostrix vaccinated) cohort and the unexposed cohort come from different time periods. With the exposed cohort from the ICD-10 era and the unexposed cohort from the ICD-9 era there is a potential risk of bias if the prevalence of adverse events is higher or lower in either exposed or unexposed cohorts due to coding variation or secular trends. This issue is not specific to KPSC but rather affects all health care organizations and similar research conducted in the U.S. However, this is not a major concern at KPSC as there is specific mapping (crosswalk) between ICD-9 and ICD-10 for all of the outcomes (36, 37). Most importantly, no matter which system is used, a comprehensive list of codes will be used to identify all potential events of interest. In addition, a review of medical records will be conducted to determine whether the events are truly incident events with onset after the index date (vaccination date for the exposed). Similarly, by using a historical cohort to identify the unexposed group to compare to a current exposed cohort, there is a concern that the baseline incidence of the selected safety endpoints will vary significantly between the Tdap (*Boostrix*) vaccination period and the historical comparison period. However, the advantage of comparing to a historical population of pregnant women during approximately 2012-2013 is that we are identifying an unvaccinated group during a period when prenatal Tdap vaccine uptake was low, making these pregnant women more representative of an unvaccinated cohort. A current unvaccinated cohort would yield a small and selective sample (given over 70% Tdap uptake) that is not representative of an unvaccinated group and would be affected by confounding by indication.

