### 3.2.4 Covariates

Covariates (Table 2) to be collected and explored include medical conditions indicative of a high-risk pregnancy and other relevant baseline characteristics. The algorithms for identification of high-risk medical conditions are described in the DMP.

Table 2. List of covariates (all covariates will be treated as categorical in the analyses)

High-risk medical condition
Thyroiditis (present/absent)
Diabetes (present/absent)
Other autoimmune diseases (present/absent)
Renal diseases(present/absent)
Cardiac diseases (present/absent)
Pre-pregnancy obesity (BMI>40: yes/no/missing)
Pre-existing hypertension (present/absent)
Rhesus sensitization (present/absent)
HIV infection (present/absent)
Syphilis infection (present/absent)
Cervical incompetence (present/absent)
Lifestyle factors
Smoking status from pregnancy start to index date (Yes/No)
Alcohol use from pregnancy start to index date (Yes/No)

Enrollment
Length of membership prior to 27 weeks gestation (but after pregnancy start) – having continuous membership from pregnancy start to index date (Yes/No)
Medicaid insurance (public health insurance: Indicator of low-income status) – any Medicaid enrollment from pregnancy start to index date (Yes/No)
Utilization
Health care utilization (receipt of medical care) from pregnancy start to index date
Any hospitalization or ED visit (Yes/No)
Number of outpatient visits (0-4/5-12/ $\geq 13$ )
Maternal Data
Number of previous pregnancies (0/1/ $\geq 2$ /Missing)
History of pregnancy loss (Yes/No)
Season of pregnancy start (September-March/April-August)
Vaccine
Receipt of other vaccines during pregnancy, e.g., influenza vaccine (Yes/No)
Receipt of vaccines containing diphtheria, tetanus toxoid or pertussis antigens within one year before pregnancy (Yes/No)
Matching variables
Race/Ethnicity (White/Black/Hispanic/Asian/Other)
Multiple gestation (Yes/No)
Age at pregnancy start (years)

Smoking status will be defined as current smoker or not. If patients reported they smoked any time from pregnancy start to index date, then they will be current smokers. Alcohol use will be defined in a similar fashion.

Length of membership prior to 27 weeks gestation (but after pregnancy start) will be defined as a dichotomous variable of having continuous membership (allowing up to a 31-day gap) from pregnancy start to index date.

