Health care utilization will be defined as any hospitalization or emergency department (ED) visit, and number of outpatient visits (0-4, 5-12,  $\geq 13$ ) from pregnancy start to index date.

Receipt of other vaccines during pregnancy will be defined as any receipt of other vaccines from pregnancy start to index date.

The covariates included in adjusted analyses will be determined by scientific relevance, association with exposure and outcome, and data availability. Specifically, we will select covariates by following these steps:

1. The distribution of covariates will be reviewed. Those covariates in the same category with rare events will likely be combined as a single covariate. For example, we might consider grouping all chronic conditions into a single covariate.
2. The data availability will be checked. If a covariate contains a large proportion that is missing, and the proportion missing is differential by exposure, then the covariate may not be included.
3. Association of covariates with exposure will be assessed. We will use standardized difference to assess the balance of covariates between exposed and unexposed cohorts. Unlike p-values, for which magnitude is highly related to sample size, standardized difference is a unified approach to quantifying the magnitude of difference between groups regardless of sample size, where an absolute value less than 0.1 is considered a negligible difference (3). We will use a SAS macro %stddiff developed by PPD and PPD (4) to calculate the standardized differences for continuous and categorical variables. Potential confounders will be determined by absolute standardized difference (ASD)  $>0.1$ .
4. Association of potential confounders (identified from step 3) with each primary endpoint will be further assessed using a change-in-estimate approach (5). Diabetes, pre-existing hypertension (except for the analysis of the preeclampsia and/or eclampsia endpoint), Medicaid insurance, and health care utilization, which are considered as the most representative prognosis factors, will be kept in the adjusted model regardless of their association with exposure and primary endpoints. For a specific endpoint, the exposure coefficient estimate from a model adjusted for the 4 above covariates will be compared with the estimate from a model adjusted for one more covariate at a time. Covariates which result in a 10% change in the exposure coefficient estimate will be selected for final adjusted analysis.

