5. All potential confounders (identified from step 3) will be included in the analyses of secondary endpoints. If the outcome is rare and the adjusted model cannot converge, problematic covariates will be removed from the model. If total counts from the two groups (i.e., sum of events in the exposed and unexposed cohorts) is less than 5, then no adjusted analysis will be performed.

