### **5.4 Limitations**

#### *Secular confounding*

Using a historical comparison group may introduce bias due to secular confounding. The events identified from a current exposed cohort and a historical unexposed cohort may differ in background rates due to care improvement, changes in diagnostic criteria, changes in health-seeking behavior, and changes in the coding system. This is an inherent limitation of using a historical comparison and needs to be acknowledged. The approach we propose, using a comprehensive list of codes to identify all potential events of interest, followed by a review of medical records to confirm the incident events, aims to minimize the bias caused by changing coding practices.

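### If health care use differs between the cohorts, the congenital anomaly models will adjust for visits counted after anomalies form, which can bias the adjusted RR

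*SAP*

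**What the plan says.** All references are to SAP Final 2.0 and Protocol Amendment 2.

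- **Covariate rule.** SAP 3.2.4 step 3 calls a covariate a potential confounder if its ASD between cohorts exceeds 0.1. Step 5 then says: "All potential confounders (identified from step 3) will be included in the analyses of secondary endpoints". Congenital anomalies are a secondary endpoint, and no passage exempts them.
- **Forced covariates.** Step 4 lists four covariates, health care utilization among them, that "will be kept in the adjusted model regardless of their association with exposure and primary endpoints". That step concerns association "with each primary endpoint will be further assessed using a change-in-estimate approach", so it does not govern the anomaly models.
- **Window.** SAP Table 2 lists "Health care utilization (receipt of medical care) from pregnancy start to index date". It has two parts: a yes/no item for hospital admission or ED attendance, and outpatient visits in three classes (0-4, 5-12, 13 or more). For the main analysis the index date is in week 27 or later.
- **Timing of the outcome.** Protocol section 7 states that "the most plausible time period for development of congenital anomalies is during early pregnancy".
- **Era.** SAP 5.4 names "changes in health-seeking behavior" among the ways the 2018-19 and 2012-13 cohorts may differ.
- **Decision rule.** Under SAP 4.3 an elevated risk is declared when the lower 95% limit of the adjusted RR is above 1, and SAP 4.5 ties signal investigation to that finding. The unadjusted RR is reported but triggers nothing.

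**The concern.** For most endpoints, utilization up to the index date is a baseline covariate, because the event must come later. For congenital anomalies the order is reversed. By the protocol's own account the anomaly is usually present before or during the window in which visits are counted. A suspected anomaly can bring extra scans, referrals or admissions, so utilization can be a consequence of the outcome.

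Step 3 lets utilization in only when it differs between cohorts, so the rule selects it exactly when it is also related to era. Conditioning on a variable that depends on both era and outcome opens a path between the two where none need exist. If use was higher in 2018-19, the adjusted RR is pulled below 1 and a real signal may be missed. If use was lower, it is pushed above 1 and a false signal becomes more likely. Because the signal rule reads only the adjusted RR, the bias acts on the one decision made for this endpoint.

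**Working it through.** **The plan's own figure.** The only computed figure is 95.7% power for the primary endpoints. It reproduces (95.71% by the score method) and has no bearing here. The documents give no utilization distribution, ASD, anomaly prevalence or anomaly-utilization link, so everything below rests on assumptions.

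**Inputs.** From the documents: 15,000 per cohort (taken as the number of infants), a Poisson model, and a signal if the lower 95% limit exceeds 1. Assumed: true RR 1; low/mid/high visits of 25/55/20% in one era, and 20/55/25% (ASD 0.15) or 15/55/30% (ASD 0.30) in the other; an anomaly multiplies the odds of mid/high visits by 1.2/1.5 (weak) or 1.5/3 (stronger).

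**Worked case.** Use fell, ASD 0.15, link 1.5/3, prevalence 3% (450 cases per cohort).

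- Unexposed 20/55/25: weights 0.20, 0.825, 0.75; sum 1.775. Cases by level: 50.7, 209.2, 190.1.
- Exposed 25/55/20: weights 0.25, 0.825, 0.60; sum 1.675. Cases by level: 67.2, 221.6, 161.2.
- Adding 14,550 non-cases per cohort in the cohort's own visit shares gives these risks by level: unexposed 1.71%, 2.55%, 4.97%; exposed 1.81%, 2.69%, 5.25%.
- Every stratum ratio is about 1.06 although the crude RR is 450/450 = 1. The Poisson model adjusted for visits gives 1.058.
- SE of log RR is about √(2/450) = 0.067. P(signal) = 1 − Φ(1.96 − log RR/SE) = 1 − Φ(1.96 − 0.84) = 13%, against 2.5%.

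**Grid for a single anomaly class.** SE is about 0.116 at 1% prevalence and 0.164 at 0.5%. Where only a share f of anomalies raises use, cases are distributed as f × (weighted shares) + (1 − f) × (cohort shares). RRs are at 1% prevalence and hardly change with prevalence.

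| Link | Share raising use | ASD | RR, use rose | RR, use fell | P(signal), use fell, 1% | same, 0.5% |
|---|---|---|---|---|---|---|
| 1.2/1.5 | all | 0.15 | 0.980 | 1.020 | 3.7% | 3.3% |
| 1.2/1.5 | all | 0.30 | 0.961 | 1.041 | 5.3% | 4.3% |
| 1.5/3 | all | 0.15 | 0.944 | 1.059 | 7.1% | 5.4% |
| 1.5/3 | all | 0.30 | 0.895 | 1.118 | 15.8% | 10.0% |
| 1.5/3 | 50% | 0.15 | 0.972 | 1.029 | 4.3% | 3.7% |
| 1.5/3 | 50% | 0.30 | 0.946 | 1.057 | 6.9% | 5.3% |
| 1.5/3 | 30% | 0.15 | 0.983 | 1.017 | 3.5% | 3.2% |
| 1.5/3 | 30% | 0.30 | 0.967 | 1.034 | 4.7% | 4.0% |

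**Second set of assumptions.** Here unexposed visits are 10/65/25%, 25% have hospital/ED use, 30-50% of anomalies are suspected before index, the odds ratios are 1.5-5 for visits and 1.5-2 for hospital/ED use, and the model adjusts for both. At ASD about 0.2 the RR is 0.90-0.98 (use rose) or 1.02-1.11 (use fell). At ASD about 0.33-0.35 it is 0.83-0.96 or 1.03-1.19. With no era difference it is 1.00. With utilization left out it is 1.00 in every null scenario, because these scenarios contain no real confounding by utilization.

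**The case against.** **Entry is conditional.** A reader might infer from step 4 that utilization is always in the anomaly models. The documents do not support that: the forced-in rule covers primary endpoints only. If the ASD is 0.1 or less, utilization does not enter and the problem does not arise. This stands.

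**The incident-case rules may remove the cases that matter.** Protocol 6.1 bars a diagnosis code for the condition before the index date, and SAP 3.2.3 requires a confirmed event to start after it. Read literally, an anomaly coded prenatally is not a case, which would weaken the path. This stands in part. How the rules apply to infant-level diagnoses is not spelled out, and an anomaly suspected before index but first coded after birth still counts.

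**The largest numbers do not apply as they stand.** A reader might infer a false-signal rate of 13-37%. That figure is for all anomalies combined at 3% prevalence. It needs every anomaly to raise prenatal use, including those found only after birth, and it needs use to have fallen, which nothing in the documents indicates. SAP Table Shell 5 marks the overall anomaly RR as not applicable, although SAP 4.3 describes RRs overall and by type.

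**Utilization may stand in for maternal risk.** The SAP treats it as a leading prognostic factor, so dropping it could leave confounding. This stands, and is the reason to keep it in a sensitivity analysis.

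**Consequences are limited.** Secondary endpoints generate hypotheses, the unadjusted RR is shown alongside, and the protocol already urges caution on anomalies. All true, but a downward bias can stop the signal rule from triggering at all.

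**Conclusion.** The concern holds conditionally. If either utilization covariate passes ASD 0.1, step 5 puts it into the anomaly models. Its window then overlaps or follows the outcome's onset, and the adjusted RR can be biased in a direction that cannot be known in advance.

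With true RR 1 and ASD 0.15-0.30, the bias is about 2-12% if every anomaly raises use and about 2-6% if 30-50% do (odds multiplied by 1.5/3). For organ-system RRs at 0.5-1% prevalence, the false-signal probability when use fell is about 3-16%, against 2.5%. Stronger assumed links give more (RR down to 0.83 or up to 1.19), and effective removal of prenatally coded anomalies gives less. These are illustrations, not estimates.

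The documents do not show that utilization will be imbalanced or which way it moved, so a spurious association is possible rather than established. Nor do they support removing every covariate measured after pregnancy start: smoking and alcohol use share the window, but the argument here does not reach them.

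**What to change.** Add to SAP 3.2.4 step 5: for congenital anomalies (by type, and overall if an RR is reported), outpatient visits and hospital/ED use counted from pregnancy start to index date are left out of the adjusted model used for the signal rule. The RR with them included is shown as a sensitivity analysis. All other covariates stay under the existing rule. Step 4 already makes an endpoint-specific exception (pre-existing hypertension for preeclampsia), so the form is familiar.

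It would help to state in the same edit how the incident-case rule treats an anomaly suspected or coded before index, and to reconcile SAP 4.3 with Table Shell 5 on whether an overall anomaly RR is reported.

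The cost is a short SAP edit and one extra model per anomaly outcome, with no new data, derived variables or chart review. The downside is that any maternal-risk confounding for which utilization is a proxy goes unadjusted in the main anomaly model. A gap between the main and sensitivity RRs would show how much depends on that choice, though not which of the two is biased.

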### 3.3 Sample Size and Power Considerations

The power computation for the primary objective was performed using PASS non-inferiority of two independent proportions using Miettinen and Nurminen method. Although the power is not based on the Poisson regression model, it is expected to reflect the power on the planned analysis since inference on proportion and incidence rate provide similar results when incidence rates are low.

The following table (Table 3) shows the power to rule out a two-fold increase considering an assumed possible design bias leading to a 1.25 relative risk increase.

To be able to make independent conclusions for each of the four primary endpoints while controlling the type I error below 2.5%, a Bonferroni adjustment will be used, i.e., each primary endpoint will be evaluated using a one-sided 0.625% (2.5% type I error / 4 primary endpoints) nominal type I error. More specifically, the upper limit of the two-sided 98.75% confidence interval (CI) will be used to make conclusions.

Considering that the four primary endpoints are expected to have an incidence rate above 1%, the power to conclude that maternal immunization is non-inferior for any primary endpoint is at least 95% and the power to conclude that maternal immunization is non-inferior for all 4 primary endpoints is at least 80% (100% - 4\*beta).

Table 3. Power to rule out a two-fold increase with 15,000 pregnant women in each cohort

Incidence rate in unvaccinated cohort	One-sided type I nominal error	True relative risk	Power	Beta
1%	0.625%	1.25	95.7%	4.3%

#### 4. ANALYSES OF OBJECTIVE

All analyses will be performed by statisticians at KPSC using the SAS statistical software package (version 9.4 or later).

##### 4.1 Description of study population

The size of the study population and subgroups for main analysis will be described, overall and by exposed and unexposed cohorts. See Appendix A, Table Shell 1 for details. The number and percentage of pregnant women with unknown pregnancy outcome, lost to follow up, and multiple gestation will also be reported.

Baseline characteristics will be described and compared between the exposed and unexposed cohorts. See Appendix A, Table Shell 2 for details. Bivariate analyses will be conducted for all covariates of interest. Continuous variables such as age in years will be summarized by mean, median, Q1, Q3, range, and standard deviation and compared using t-tests; categorical variables will be summarized by frequency and percentage and compared using chi-square tests or Fisher's exact test, as appropriate. Absolute standardized difference will be calculated to assess the balance of covariates. Potential confounders will be determined based on bivariate analyses and scientific relevance (see Section 3.2.4).

Birth outcomes captured among KPSC born infants (birth weight, length, head circumference, and Apgar scores) will be described for exposed and unexposed cohorts. See Appendix A, Table Shell 3 for details.

##### 4.2 Analyses of primary endpoints

We will calculate crude incidence and 95% CI for each primary endpoint for the exposed and unexposed cohorts. Unadjusted and adjusted RR with two-sided 98.75% CI will be estimated comparing the exposed cohort to the unexposed cohort, accounting for multiple comparisons.

Analysis of primary endpoints will be used to evaluate the safety of Boostrix vaccination and concluded to be non-inferior if the upper limit of the 98.75% CI for the adjusted relative risk is below 2.

Analyses of preeclampsia and/or eclampsia and intra-uterine infection will be performed on all pregnant women eligible for main analysis. For events identified any time after the index date (e.g., preeclampsia and/or eclampsia and intra-uterine infection), the incidence will consist of the total number of women with the condition in the numerator and the total person time in the denominator. The person-year for a pregnant woman will be the time from the index date to the date of each adverse event, end of the pregnancy, or disenrollment, whichever comes first. The unadjusted and adjusted relative risk with 98.75% CI will be estimated by Poisson regression models accounting for the follow-up time without and with adjustment for potential confounders. If the outcome is common (i.e., incidence > 2%), a Poisson regression model with a robust error variance will be used to estimate the relative risk (6). The robust Poisson regression will be performed using the SAS Proc GENMOD procedure with the REPEATED statement subject= Patient\_ID.

Analysis of SGA will be performed on live singleton infants born in KPSC hospitals, while analysis of preterm delivery will be performed on pregnant women with live births, and with an index date prior to 37 weeks gestation. For events identified at delivery (e.g., SGA and preterm delivery), the incidence will consist of the total number of women or infants with the condition in the numerator and the number of women or infants for whom the condition can be assessed in the denominator. The unadjusted and adjusted relative risk with 98.75% CI will be estimated by Poisson regression models with robust error variances without and with adjustment for potential confounders. The planned methods of analysis by primary endpoint are outlined in Table 4. See Appendix A, Table Shell 4 for details.

Table 4. Analytic population and statistical methods by primary endpoint

Primary endpoints	Analytic population	Statistical Methods
Preeclampsia and/or eclampsia	All pregnant women eligible for main analysis	Adjusted Poisson regression model accounting for follow up time, with robust variance estimate
Intra-uterine infections	All pregnant women eligible for main analysis	Adjusted Poisson regression model accounting for follow up time, with robust variance estimate
SGA	KPSC live born infant, singleton only*	Adjusted Poisson regression model, with robust variance estimate
Preterm delivery	Pregnant women with live birth, with index date prior to 37 weeks gestation	Adjusted Poisson regression model, with robust variance estimate

\*There are no well accepted SGA metrics for infants born to pregnant women with multiple gestation

Limiting analyses of endpoints to subgroups (e.g., KPSC live born infant) may cause matches to be broken, although we expect the proportions of non-live births and non-KPSC births to be small.

The matching variables will be included in the adjusted models of analyses of SGA and preterm delivery. Age at pregnancy start will be adjusted as a categorical variable (<24/25-34/≥35 years).

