6.2.2. Analysis of primary and secondary objectives (amended 12 November 2019)

Demographics and pregnancy information will be compared between the exposed and unexposed cohorts. Bivariate analyses will be conducted for all covariates of interest. Continuous variables will be summarized by means, medians, ranges, and standard deviations and compared using t-tests; categorical variables will be summarized by frequency distributions and compared using chi-square tests for the exposed and unexposed groups. Potential confounders will be determined based on bivariate analyses and scientific relevance.

For events identified at delivery such as SGA, preterm delivery, ***and transfusion during delivery hospitalization***, we will calculate crude incidence and 95% confidence intervals (CI) for each adverse event for the exposed and unexposed groups. The incidence of each maternal adverse event during pregnancy will be calculated separately and will consist of the total number of women with the condition in the numerator and the number of women for whom the condition can be assessed in the denominator. The adjusted relative risk with CI will be estimated by a Poisson regression model with adjustment for potential confounders. If the outcome is common (i.e., incidence > 2%), a Poisson regression model with robust variance estimation will be used to estimate the relative risk (34). For primary endpoints, a two-sided 98.75% CI will be used for the relative risk with multiple comparison adjustment, while for secondary endpoints a two-sided 95% CI will be used.

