### **3.2 Study population, exposures, outcomes and covariates**

#### **3.2.1 Study populations/subgroups**

##### *Study population for main analysis (primary objective and secondary objective #1)*

- Pregnant women received prenatal care at KPSC
- Exposed cohort: vaccinated with Boostrix on the 1st day of the 27th week of pregnancy or later during the pregnancy and were not vaccinated with any other Tdap vaccine at any other time during the pregnancy or
- Unexposed cohort: pregnant at least one day during the approximate estimated period between 1/1/2012-12/31/2013 and did not receive any Tdap vaccine during the pregnancy
- Continuous membership (allowing up to a 31-day gap) between the 1st day of the 27th week of pregnancy and the index (vaccination) date

The unexposed cohort will be 1:1 matched to the exposed cohort on age at pregnancy start ( $\pm 1$  year), race/ethnicity (White, Black, Hispanic, Asian, and Other), and multiple gestation (yes/no). Every unexposed woman will be assigned an index date that is determined by the number of days from pregnancy start to the Boostrix vaccination date of her matched exposed woman. The same number of days calculated in the exposed woman will be added to the pregnancy start of the unexposed woman to determine her index date.

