The algorithms for identification of primary and secondary endpoints are described in the DMP. Except SGA, preterm delivery, and transfusion during delivery hospitalization, AEs identified through the algorithms will be chart reviewed to confirm the diagnosis and the onset (when applicable). Analyses of endpoints will be based on confirmed cases. For AEs with a chart-reviewed onset date, the event start date will be the onset date; for AEs without a chart-reviewed onset date (unknown or inapplicable), the event start date will be the earliest confirmed diagnosis date. To be a confirmed case, the event start date needs to be after the index date. Some AEs might be diagnosed during the delivery hospitalization, and have an event start date after the delivery date. For pre-eclampsia and/or eclampsia, intra-uterine infections, and poor fetal growth, the event date needs to be on or before the delivery date. For placental abruption and PPROM, if the event start date is after the delivery date, the delivery date will be used as the event start date.

SGA will be defined based on reference values derived by Talge et al. with a cut-off of <10th percentile (1). Talge et al used 2009-2010 US natality data and corrected for likely errors in gestational age dating to yield an up-to-date birth weight for gestational age reference. The

evaluation of SGA is limited to singleton births because the reference values for SGA definition are established based on singleton births.

Stillbirth/fetal death has a number of different and legally mandated definitions (2). This study will use ACOG's definition which defines stillbirth/fetal deaths at 20 completed weeks gestation or greater (if the gestational age is known). Maternal death will include all non-accidental deaths while pregnant or within 42 days of end of pregnancy. Neonatal death will include deaths within 28 days of birth among KPSC live born infants.

For a multiple gestation pregnancy, the pregnancy outcome will be recorded for each fetus, while the endpoint will be defined by the worst scenario. For examples, the woman will be considered to have a pre-term delivery, if any fetus was delivered pre-term after the index date. The woman will also be considered to have spontaneous abortion, therapeutic abortion, or stillbirth/fetal death if any fetus experienced these pregnancy outcomes after the index date.

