### *Quality control steps*

During the analysis, when analytic data are created and analyzed, the following quality control steps will be performed by the study statisticians as appropriate:

1. Read study protocol, DMP, and the statistical analysis plan. Communicate with the principal investigator, senior statistician, and study team with any questions regarding study design and analysis plan. Document any decisions related to statistical analysis.
2. Check data quality (sample size, duplicates, range of values, number of missings, proper data type and format, inconsistency, etc.). Any aberrant data that have been missed by data cleaning and discovered by the statistician will be described in the results table.
3. Participate in 2 days of CDISC training on SDTM, ADaM, and Define.xml. Participate in 1-day CDISC study-specific workshop. Become familiar with SDTM and ADaM data standards. Work with CDISC standards consultant to develop ADaM specifications and create ADaM datasets according to SAP.
4. Develop SAS programs for analysis. Programs will include a program header and section headers. The program header contains information on the name, location, and purpose of the program, a list of prerequisite programs if applicable, a list of input datasets with full path, a list of output datasets, and a history log. Revision of the program will be noted in the history log to capture the change made, the change date, identification of the individual making the change, and type of change (e.g. modification, addition, removal). Each program might have several sections

executing various analytic steps. Programs will be annotated with comments that describe the intent or purpose.

5. Perform statistical analysis. Use appropriate procedures and tests. SAS logs and outputs will be reviewed for any warnings, error messages, and model convergence issues. Organize the output into results tables. When possible, automate the generation of results tables to minimize the need to copy/paste. Proofread the results tables to prevent any copy/paste and editing errors. SAS logs and outputs will be saved.

6. Use established SAS macro. Use established SAS macros for analyses, including but not limited to the macro for creating baseline covariate tables and the macro for calculating standardized difference.

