#### *Program review*

All SAS analysis programs, logs and outputs will be reviewed by a second statistician. The second statistician will review the program logic against the analysis requirements. Comments from the second statistician will be documented and followed up until resolved.

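### The age bands in SAP 4.2 (<24/25-34/≥35) give women aged 24 no level in the adjusted SGA and preterm-delivery models

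*SAP*

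**What the plan says.** SAP section 4.2 puts the matching variables into the adjusted models for SGA and preterm delivery and then fixes the form of age: "Age at pregnancy start will be adjusted as a categorical variable (<24/25-34/≥35 years". The decision rests on these models, since each primary endpoint is "concluded to be non-inferior if the upper limit of the 98.75% CI for the adjusted relative risk is below 2".

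The other places that bear on age are these:

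- SAP 3.2.4, Table 2, lists age at pregnancy start in years, under a title saying that "all covariates will be treated as categorical in the analyses".
- SAP 3.2.1 has the unexposed cohort "1:1 matched to the exposed cohort on age at pregnancy start", within one year.
- SAP 5.1 plans no covariate imputation. It provides a separate missing level only for number of previous pregnancies and pre-pregnancy weight.
- SAP Appendix A, Table Shell 10, bands age at pregnancy start as <18, 18-24, 25-34 and ≥35.
- SAP Final 1.0, section 4.2, has the same <24/25-34/≥35 bands, so Final 2.0 carried them over.

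**The concern.** The first band stops below 24 and the second starts at 25, so a woman aged 24 at pregnancy start has no level. Because age enters only as a categorical term, no continuous term can place her. The missing-data section does not help either, since her age is known.

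A programmer therefore has two routes. If the bands are coded literally and age 24 is left blank, these women drop out of the adjusted model. The adjusted and unadjusted relative risks in the same row of Table Shell 4 would then rest on different women, and the adjusted analysis would no longer cover the population named in SAP Table 4. A woman aged 24 may also be matched to one aged 23 or 25, so one member of a pair could be lost and the other kept. The second route is to choose a band, which is an unspecified choice made during the analysis. Either way, the model that decides two of the four primary endpoints is not fully specified.

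**Working it through.** **1. Coverage of the bands.** Every whole-year age from 12 to 55 was tested.

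| Bands | Ages in no band |
|---|---|
| <24 / 25-34 / ≥35 (SAP 4.2) | 24 |
| <18 / 18-24 / 25-34 / ≥35 (Table Shell 10) | none |
| <25 / 25-34 / ≥35 | none |

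**2. The SAP's own power figure.** Inputs from SAP 3.3 are 15,000 per cohort, incidence 1%, true RR 1.25, margin 2 and one-sided alpha 2.5%/4 = 0.625% (z = 2.498). The method is the Miettinen-Nurminen ratio test, with

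power = Φ[(2·p0 − p1 − z·SE0)/SE1].

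Here p0 = 0.01 and p1 = 0.0125. SE0 is 0.001723, from the proportions constrained to a ratio of 2, and SE1 is 0.001861. The bracket is (0.0075 − 2.498 × 0.001723)/0.001861 = 1.718, so power is 95.7%. This reproduces SAP Table 3.

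**3. Share aged 24 (an assumption).** Protocol Table 2 gives age at vaccination in bands only: 5,785 of 19,804 aged 15-26 and 10,858 aged 27-35. A woman aged 24 at pregnancy start is 24 or 25 at vaccination, so she is in the 15-26 band.

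- Even spread: 5,785/12/19,804 = 2.4%, about 365 per 15,000.
- Linear rise over ages 15-26 (weights 1 to 12, sum 78): 5,785 × 10/78/19,804 = 3.7% (about 562) using age 24, and 5,785 × 11/78/19,804 = 4.1% (about 618) using age 25.
- Loose ceiling, the average year of the 27-35 band: 10,858/9/19,804 = 6.1%, about 914.

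**4. Effect if these women drop out of both cohorts.** Losing the same share from each cohort is approximate because of the one-year matching caliper. Expected upper limit = 1.25 × exp(2.498 × SE), with SE the unadjusted standard error of the log RR. At 2% and 15,000, SE = √(0.975/375 + 0.98/300) = 0.0766.

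| Share lost | Power, 1% incidence | Power, 2% | Upper limit, 2% | Upper limit, 10% | SE ratio 1/√(1−share) |
|---|---|---|---|---|---|
| none | 95.7% | 99.97% | 1.514 | 1.356 | 1 |
| 2.4% | 95.2% | 99.96% | 1.517 | 1.358 | 1.012 |
| 3.7%-4.1% | 95.0%-94.9% | 99.95% | 1.519-1.520 | 1.358-1.359 | 1.019-1.021 |
| 6.1% | 94.4% | 99.94% | 1.523 | 1.360 | 1.032 |

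At 5% and 10% incidence, power is 100.0% in every row.

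**5. Preterm delivery.** This model needs an index date before 37 weeks. Protocol section 3.2 (Table 4 and its text) gives 15,000 × 18,611/19,554 = 14,277 per cohort, before the live-birth restriction. The losses are about 348, 535-588 and 870. At 2% incidence, power is 99.95% with no loss and about 99.9% at the ceiling (0.99948 to 0.99905).

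**6. Which incidence applies.** The SAP expects all four primary endpoints above 1%. The 2% row is the more relevant one. SGA is defined "with a cut-off of <10 th percentile", and both models are assigned robust variance, which the protocol ties to common outcomes: "If the outcome is common (i.e., incidence > 2%), a Poisson regression model with robust variance estimation will be used".

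**The case against.** The strongest case against is that this is a typing error of no consequence. The next band starts at 25 and Table Shell 10 cuts at 25, so most statisticians would read the first band as under 25. Loss of the women is also not certain. In SAS, a format with these ranges would normally leave 24 as a level of its own, and an IF/ELSE chain ending in a plain ELSE would put these women in the last band. The SAP also has controls: "Check data quality (sample size, duplicates, range of values, number of missings" and so on, and "The second statistician will review the program logic against the analysis requirements". Deviations must be documented, so a few hundred women missing from one model would probably be noticed. Finally, the share aged 24 is assumed, and the linear-rise weights have no source in the documents.

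Much of this stands. Exclusion depends on coding that the documents do not show, the controls make a silent loss less likely, and the effect is small under every assumption tried. It does not remove the defect. The different codings put women aged 24 in different places, and the SAP does not choose among them. The second statistician checks programs against the stated requirement, and here the requirement itself has the gap. Table Shell 10 describes signaled events and does not govern the primary models, so it shows likely intent but does not correct section 4.2.

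**Conclusion.** The point holds. The current SAP leaves age 24 without a level in the adjusted SGA and preterm-delivery models, and no other text assigns it. That a cut at 25 was intended is an inference from the adjacent band and Table Shell 10, which the sponsor can confirm.

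If the women are dropped, the loss is roughly 2% to 4% of each cohort, and 6% at most, on assumed age distributions. At the 1% reference case the cost is about one percentage point of power or less (1.3 points at the ceiling). At 2% incidence it is under 0.05 point, and the expected upper limit stays far below 2. No primary conclusion is shown to be at risk and no bias is shown. The reason to act is that the confirmatory model should be fully specified and should include every eligible woman, and here that is free.

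**What to change.** In SAP section 4.2, change the bands to <25/25-34/≥35, in line with the cut at 25 in Table Shell 10. Every whole-year age then falls in exactly one band. The cost is one character of SAP text and the matching line of code, with no new data and no extra degrees of freedom. Make the change before the adjusted models are run, so that it does not have to be recorded as an analysis deviation.
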